3.4 Duration of Study Treatment

Patients will be treated until disease progression per PCWG3/RECIST 1.1 criteria, confirmed by repeat scans performed ≥ 4 weeks later, unacceptable toxicity, or patient withdrawal, whichever occurs first.

Patients with PSA-only progression in absence of radiographic or unequivocal clinical progression should remain on study treatment.

3.5 Subject Replacement

All subjects who receive the priming dose of ^{177}Lu -PSMA treatment will be analyzed for study outcomes.

Subjects who withdraw from study participation prior to receiving dose of ^{177}Lu -PSMA-617 will be not be evaluable and will be replaced.

3.6 Study Timeline

3.6.1 Primary Completion

The study is anticipated to accrue 2-3 patients per month for an estimated accrual period of 21 months. The study is expected to reach completion for analysis of primary and secondary endpoints approximately 36 months from first patient enrolled.

4 Study Treatment

Treatment regimen

^{177}Lu -labeled PSMA is a PSMA-targeted radioligand that will be produced under Current Good Manufacturing Practice (CGMP) regulations.

In **Part A** of the study, patients will be enrolled in sequential fashion to one of three treatment schedules with respect to timing of ^{177}Lu -PSMA-617 in relation to first dose of pembrolizumab (6 evaluable patients per schedule):

Schedule 1) Priming dose of ^{177}Lu -PSMA-617 administered on Cycle 1 Day 1 followed by pembrolizumab on Cycle 2 Day 1.

Schedule 2) Priming dose of ^{177}Lu -PSMA-617 administered concurrently with initiation of pembrolizumab on Cycle 1 Day 1.

Schedule 3) Priming dose of ^{177}Lu -PSMA-617 administered on Cycle 1 Day 1 following initiation of pembrolizumab on Cycle 1 Day -21.

Pembrolizumab will be given at the FDA approved dose of 200 mg via IV every 3 weeks.

Dose-limiting toxicity data, additional safety data beyond Cycle 2 where available, along with efficacy and pharmacodynamic data, will be utilized to determine the recommended phase 2 dose and schedule of ^{177}Lu -PSMA-617 in combination with pembrolizumab to be utilized in Part B of the study.

4.1 ^{177}Lu -PSMA-617

4.1.1 Chemical and physical characteristics

^{177}Lu -PSMA-617 contains a radionuclide (^{177}Lu) chelated to PSMA, a PSMA ligand consisting of a Glu-urea motif and DOTA chelator connected by a lipophilic linker.

Lutetium (^{177}Lu) decays to stable hafnium (^{177}Hf) with a half-life of 6.7 days, by emitting β -radiation with a maximum energy of 0.498 MeV and photonic radiations (γ) of 0.208 MeV (11.0%) and 0.113 MeV (6.4%). The main radiations are detailed in **Table 1**, and physical decay summarized in **Table 2**.

Radiation	Energy (keV)	$^{177}\beta\%$	$^{177}\gamma\%$
β^-	176.5	12.2	-
β^-	248.1	0.05	-
β^-	384.9	9.1	-
β^-	497.8	78.6	-
γ	71.6	-	0.15

Y	112.9	-	6.40
Y	136.7	-	0.05
Y	208.4	-	11.0
Y	249.7	-	0.21
Y	321.3	-	0.22

Table 1. ^{177}Lu main radiation.

Hours	Fraction Remaining	Hours	Fraction Remaining
0	1.000	48 (2 days)	0.813
1	0.996	72 (3 days)	0.733
2	0.991	168 (7 days)	0.485
5	0.979	336 (14 days)	0.235
10	0.958	720 (30 days)	0.045
24 (1 day)	0.902	1080 (45 days)	0.010

Table 2. Physical decay chart for ^{177}Lu .

4.1.2 Drug preparation

Administration procedures should be carried out in a way to minimize risk of contamination from the medicinal product and accidental irradiation of the operators. It is necessary to wear waterproof gloves and suitable effective protection when handling ^{177}Lu -PSMA-617.

Flow valves should be manipulated aseptically when connecting them to the infusion system.

Any unused medicinal product or waste material should be disposed of in accordance with local and federal laws.

The solution should be inspected visually prior to use, and only clear colorless to yellowish solutions free of visible particles should be used. The visual inspection of the solution should be performed under a shielded screen for radioprotection purposes.

The amount of radioactivity in the radiopharmaceutical vial must be measured with an appropriate and calibrated device prior to infusion in order to confirm that the actual amount of radioactivity to be administered is equal to the planned amount at the infusion time.

4.1.3 Patient preparation

Patient should be encouraged to drink a sufficient amount of water necessary to urinate every hour on the day of infusion and the day after. Patient should be encouraged to defecate every day and to use laxative if needed.

The doctor will explain to the patient the general recommendations and precautions that should be followed to limit radiation exposure to third parties.

To avoid treatment-related nausea and vomiting, it is recommended to inject an intravenous bolus of 5-HT3 receptor antagonist (e.g. ondansetron 8mg) 30 minutes before the start of ¹⁷⁷Lu-PSMA infusion.

4.1.4 Concomitant hydration (renal protection)

Concomitant infusion of intravenous fluids is required for renal protection. This infusion should start 30 minutes before the start of ¹⁷⁷Lu-PSMA-617. 500 – 1000 mL of normal saline should be administered between 250-500 mLs per hour. During the administration of IV fluids, the patient should be encouraged to urinate as frequently as possible.

4.1.5 Method of administration

¹⁷⁷Lu-PSMA is a ready to use single dose vial.

¹⁷⁷Lu-PSMA must be administered by slow intravenous infusion, over a 20 to 30-minute time span (see Appendix 4 for administration method examples).

¹⁷⁷Lu-PSMA must not be injected as a bolus.

The following table summarizes the required procedure.

Table 5. ¹⁷⁷Lu-PSMA administration procedure

Product to inject	Start time (hr) (+/- 30 min)	Infusion rate* (mL/h)	Duration
5-HT3 receptor antagonist (e.g. ondansetron 8mg)**	0	Bolus	-
Hydration (normal saline)	0	250—550	-
¹⁷⁷ Lu-PSMA	0.5	-	20-30 minutes

* Infusion rates may be reduced at the discretion of the physician.

** Additional prophylactic antiemetic regimen may be given at the discretion of the treating physician as clinically indicated (e.g. Prochlorperazine, Aprepitant, Lorazepam).

After the administration is completed, the infusion line and ^{177}Lu -PSMA vial must be immediately flushed with at least 25 mL of sodium chloride 9 mg/mL solution for injection, unless the infusion method used already requires NaCl to flow through the vial and the line.

4.1.6 Dose Limiting Toxicities and Criteria for Dose De-Escalation

The starting dose level of ^{177}Lu -PSMA-617 is 7.4 GBq (+/- 15%).

Patients will be assessed for dose-limiting toxicities during Cycle 1 and 2 for patients enrolled in Part A of the study, defined as any of the following AEs occurring during Cycle 1 or 2:

- Any non-hematologic treatment-related AE \geq Grade 3, with the exceptions of Grade 3 nausea, vomiting, diarrhea, constipation, fever, fatigue, skin rash, or non-clinically significant laboratory abnormality that resolves to Grade \leq 2 within 72 hours with optimal medical management.
- Grade 4 thrombocytopenia, or Grade 3 thrombocytopenia with Grade > 1 bleeding or requirement for platelet transfusion.
- Grade 4 neutropenia lasting for > 5 consecutive days
- Grade ≥ 3 febrile neutropenia.

6 evaluable patients will be enrolled in each of the three cohorts in sequential fashion in Part A of the study. If the DLT frequency is $\geq 33\%$ for a particular cohort, that dosing schedule will be determined to be non-tolerable and the next schedule will be evaluated. In addition, if the DLT frequency attributable specifically to ^{177}Lu -PSMA-617 is $\geq 33\%$ after 6 or more evaluable patients are enrolled in Part A of the study, accrual will be temporarily halted and the dose of ^{177}Lu -PSMA-617 will be reduced to Dose Level -1 (4 GBq +/- 15%) for the remainder of patients enrolled on study. If the DLT frequency attributable to ^{177}Lu -PSMA-617 at Dose Level -1 is $\geq 33\%$ after 6 or more patients are treated at Dose Level -1, study accrual will be halted.

Patients who discontinue study for reasons other than treatment related toxicity during prior to the completion of two cycles of therapy, or those who discontinue study prior to receiving priming dose of ^{177}Lu -PSMA-617, will be considered inevaluable for purposes of DLT determination.

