With respect to dose schedule, the majority of trials combining radiation-based treatment with immune checkpoint inhibition have utilized schedules in which the priming dose of radiation is given prior to or concurrently with initiation of immune checkpoint inhibition. However the optimal timing of radiation priming is not well established in prospective clinical trials, and rationale arguments support giving priming radiation before or after the first dose of immune checkpoint inhibition. In the current study, three schedules will be explored in Part A, with priming ^{177}Lu -PSMA-617 delivered prior to, concurrently, or following the first dose of pembrolizumab, respectively. The aggregate safety, efficacy, and immunologic parameters observed in Part A will be utilized to determine the optimal dose/schedule of ^{177}Lu -PSMA-617 in conjunction with pembrolizumab to be further evaluated in Part B of the study.

As of June 1, 2020, 14 patients have been enrolled in Part A of the study. There has been one dose-limiting toxicity (Grade 3 inflammatory arthritis in Schedule 2) observed to date. There have not been any other Grade ≥ 3 immune related adverse events outside of this DLT, nor any Grade ≥ 3 hematologic toxicities attributable to the priming dose of ^{177}Lu -PSMA-617. Encouraging preliminary evidence of efficacy has been observed with objective response rate by RECIST 1.1 criteria of 3/6 patients (50%), and the median duration of response has not been reached. Below shows a PSA plot of the two of the patients with ongoing objective + PSA90 responses to treatment.

Given the encouraging preliminary efficacy and safety data, as well as to obtain additional correlative samples including paired tumor biopsies that may help to further identify patients more likely to respond to treatment, we will increase the pre-specified Dose Expansion sample size from 12 to 25 patients.

2 Objectives and Endpoints of the Study

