3.1 Characteristics

This is a single-center Phase 1b open-label, study of PSMA-targeted radionuclide therapy with ¹⁷⁷Lu-PSMA-617 in combination with pembrolizumab in patients with mCRPC who have previously progressed on at least one prior androgen pathway inhibitor (e.g. abiraterone, enzalutamide, apalutamide). Patients must have at least three metastatic lesions which are PSMA-avid on baseline ⁶⁸Ga-PSMA-11 PET imaging.

In **Part A** of the study, patients will be enrolled in sequential fashion to one of treatment schedules with respect to timing of ¹⁷⁷Lu-PSMA-617 in relation to first dose of pembrolizumab (N = 6 evaluable patients per schedule):

Schedule 1) Priming dose of ¹⁷⁷Lu-PSMA-617 administered on Cycle 1 Day 1 followed by pembrolizumab 200 mg IV q 21 days starting Cycle 2 Day 1.

Schedule 2) Priming dose of ¹⁷⁷Lu-PSMA-617 administered concurrently with initiation of pembrolizumab on Cycle 1 Day 1.

Schedule 3) Priming dose of ¹⁷⁷Lu-PSMA-617 administered on Cycle 1 Day 1 following initiation of pembrolizumab on Cycle 1 Day -21.

The priming dose of ¹⁷⁷Lu-PSMA-617 will be 7.4 +/- 15% GBq, which is the recommended phase 3 dose of the agent. If the DLT frequency exceeds 33% including patients across the three schedules, Dose Level -1 of ¹⁷⁷Lu-PSMA-617 will be investigated (4 Gbq +/- 15%).

6 evaluable patients will be enrolled in each of the three cohorts in sequential fashion in Part A of the study. The DLT window will be Cycle 1 + Cycle 2. If the DLT frequency is \geq 33% for a

particular cohort, that dosing schedule will be determined to be non-tolerable and the next schedule will be evaluated. In addition, if the DLT frequency attributable specifically to Lu-PSMA-617 is $\geq 33\%$ after 6 or more evaluable patients are enrolled in Part A of the study, the dose of Lu-PSMA-617 will be reduced to Dose Level -1 (4 GBq +/- 15%) for the remainder of patients enrolled on study. If the DLT frequency attributable to Lu-PSMA-617 at Dose Level -1 is $\geq 33\%$ after 6 or more patients are treated at Dose Level -1, study accrual will be halted.

Using the data obtained in Part A, the recommended phase 2 dose and schedule of ^{177}Lu -PSMA-617 will be determined by the DSMC and Principal Investigator using a combination of safety, efficacy, and immunologic effects of treatment from the first two cycles (and additional cycles of treatment when available).

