6.3.2.5 Attribution of Adverse Events

The toxicity profiles of the two investigational agents are largely non-overlapping, which should facilitate adverse event attribution to the specific agent. Hematologic toxicity will be attributed to Lu-PSMA-617 unless there is clear evidence of autoimmune cytopenia. Xerostomia will be attributed to Lu-PSMA-617 unless clear evidence of other autoimmune sequelae. Conversely, immune-related AEs such as colitis, pneumonitis, transaminitis will be attributed to pembrolizumab. In cases where attribution to a specific agent is not possible, the timing of onset in relation to timing of initiation of Lu-PSMA and pembrolizumab will be utilized. In cases where adverse event attribution to a single agent is not possible, attribution will be to study regimen

and dose modification criteria for both agents will be utilized. The PI will have the final determination of adverse event attribution that is reported.

AEs associated with pembrolizumab exposure, including coadministration with additional compounds, may represent an immunologic aetiology. These immune-related AEs (irAEs) may occur shortly after the first dose or several months after the last dose of pembrolizumab/combination treatment and may affect more than one body system simultaneously. Therefore, early recognition and initiation of treatment is critical to reduce complications. Based on existing clinical study data, most irAEs were reversible and could be managed with interruptions of pembrolizumab/combination treatment, administration of corticosteroids and/or other supportive care. For suspected irAEs, ensure adequate evaluation to confirm etiology or exclude other causes. Additional procedures or tests such as bronchoscopy, endoscopy, skin biopsy may be included as part of the evaluation. Dose modification and toxicity management guidelines for irAEs associated with pembrolizumab/combination treatment are provided in AE Table.

Attribution of Toxicity:

When study interventions are administered in combination, attribution of an adverse event to a single component is likely to be difficult. Therefore, while the investigator may attribute a toxicity event [to the combination, to ¹⁷⁷Lu-PSMA-617 alone or to pembrolizumab alone, for adverse events listed in AE Table 6, both interventions must be held according to the criteria in AE Table Dose Modification and Toxicity Management Guidelines for Immune-Related Adverse Events Associated with Pembrolizumab.

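### The DLT list cannot count treatment-related anaemia by itself, even at Grade 4 or 5; the practical effect is small and the repair is cheap

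*Combined protocol and SAP*

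**What the plan says.** Section 4.1.6, repeated in the synopsis under Safety Assessments, gives four DLT items for Cycles 1 and 2:

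1. "Any non-hematologic treatment-related AE" of Grade 3 or higher, with some Grade 3 exceptions.
2. "Grade 4 thrombocytopenia, or Grade 3 thrombocytopenia with Grade > 1 bleeding or requirement for platelet transfusion".
3. Grade 4 neutropenia lasting more than 5 consecutive days.
4. Febrile neutropenia of Grade 3 or higher.

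There is no item for other Grade 4 or 5 events and none for investigator judgement.

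Four rules use the DLT frequency:

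- **Schedule rule (3.1, 4.1.6):** a schedule is non-tolerable at 33% or more in its cohort of 6.
- **Pooled dose rule:** 4.1.6 reduces the dose "if the DLT frequency attributable specifically to" 177Lu-PSMA-617 reaches 33% or more once 6 or more Part A patients are evaluable. Section 3.1 also has an all-DLT wording: "If the DLT frequency exceeds 33% including patients across the three schedules".
- **Halt at Dose Level -1:** 33% or more of patients treated at that level.
- **Part B look (8.3):** accrual stops if the frequency exceeds 33% after 6 patients. Section 4.1.6 writes the list for Part A patients, and 8.3 does not say which list Part B uses.

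Section 4.1.8 lists anaemia as a reaction to 177Lu-PSMA-617. Section 6.3.2.5 sets the default attribution: "Hematologic toxicity will be attributed to Lu-PSMA-617 unless there is clear evidence of autoimmune cytopenia".

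**The concern.** Anaemia is haematologic, so item 1 excludes it, and items 2 to 4 name only platelets and neutrophils. The protocol expects this toxicity and assigns it to the radioligand by default, yet the formal count cannot register it. Taken to the extreme, six of six patients with Grade 4 anaemia and no other listed event would score 0/6. A haematologic death outside febrile neutropenia is in the same position unless another listed item is also met.

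The evaluability rule in 4.1.6 works in the same direction. Early discontinuation makes a patient inevaluable only when the reason is something other than treatment-related toxicity. A patient who stops early for treatment-related anaemia therefore stays in the denominator as a non-DLT.

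At stake is whether a pre-specified safety rule could be passed when a life-threatening treatment-related event should have counted against it.

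**Working it through.** **Plan's own figures.** The plan states no operating characteristics for its DLT rules. Its one calculated figure, 93% power for Part B response, reproduces at 92.6% (exact binomial, 7 or more of 25) and has no bearing here.

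**Inputs.** Section 1.7.1 reports 14 Part A patients enrolled by 1 June 2020. "There has been one dose-limiting toxicity (Grade 3 inflammatory arthritis in Schedule 2) observed to date". It also reports no Grade 3 or higher "hematologic toxicities attributable to the priming dose of" 177Lu-PSMA-617. Part A is planned at 18, so 18 - 14 = 4 remain. Enrolment is sequential in sixes, so patients 13 to 18 form the last cohort and two of them are already in. This assumes the 14 are evaluable, past their window and not replaced.

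**Signal so far.** 0/14 attributable events gives a one-sided 95% upper bound of 1 - 0.05^(1/14) = 19.3%. The denominator is enrolled patients, because the evaluable number is not given.

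**Pooled dose rule.** The one DLT is of immune type, and 6.3.2.5 says "immune-related AEs such as colitis, pneumonitis, transaminitis will be attributed to pembrolizumab", so the Lu-attributable count is taken as 0. If anaemia counted and all four remaining patients had it, the rate would run 1/15 = 6.7%, 2/16 = 12.5%, 3/17 = 17.6%, 4/18 = 22.2%. Counting all DLTs, the maximum is (1 + 4)/18 = 27.8%. The rule needs 6/18 = 33.3%, so neither version can fire, and the halt at Dose Level -1, which depends on it, is not reached. If k of the 14 were replaced, the Lu-attributable maximum becomes (4 + k)/18. Two replacements would just allow 6/18, but only if every remaining patient had an event.

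**Schedule rule, last cohort.** 2/6 = 33.3% meets the threshold. The only DLT was in Schedule 2, so two of the last four patients would be needed.

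**Part B look.** 2/6 = 33.3% exceeds 33% read literally; 3/6 is needed if one third is meant.

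**Probabilities.** The documents give no usable single-dose rate of Grade 4-5 anaemia, so a rate q of 1% to 10% is an assumption. Binomial tails for anaemia alone:

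| q | 2 or more of 6 | 3 or more of 6 | 2 or more of 4 |
|---|---|---|---|
| 1% | 0.15% | 0.002% | 0.06% |
| 2% | 0.57% | 0.02% | 0.23% |
| 5% | 3.3% | 0.22% | 1.4% |
| 10% | 11.4% | 1.6% | 5.2% |

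Anaemia could also combine with a listed DLT. Taking the listed-DLT rate as 1/14 and assuming independence, the per-patient rate is 1 - (13/14)(1 - q). The chance of 2 or more of 6 is then 6.3% at q = 0, 15.1% at q = 5% and 25.7% at q = 10%. For 2 or more of 4 it is 2.8%, 7.1% and 12.9%.

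**The case against.** The strongest reply is that the formal count does not decide alone. Sections 3.1 and 8.4.1 base the recommended dose and schedule on aggregate safety and efficacy data, and 3.1 gives the choice to the Data and Safety Monitoring Committee (DSMC) and Principal Investigator. No schedule follows Schedule 3, so in the last cohort the rule only bars that schedule from selection, which those parties can do anyway. This stands and is the main reason the effect is small.

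Item 1 would also still count a Grade 3 or higher non-haematologic consequence of anaemia. This stands too: the gap is confined to anaemia without such a consequence.

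Several stronger readings are tempting, and the documents do not support them:

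- **That severe anaemia would go unseen.** Appendix 2 has monthly Site Committee review of Grade 3-5 events and ongoing DSMC review of serious suspected reactions. Section 6.6 takes treatment-related deaths during treatment or within 30 days of the last dose to the DSMC Chair within 1 business day. Section 6.2 requires weekly blood counts after Grade 3 or higher haematologic toxicity.
- **That no other rate-based trigger exists.** Appendix 2 has a heading on increases in adverse event rates whose text is not in the copy available here, so this cannot be judged.
- **That leaving out Grade 3 anaemia is an error.** The list is selective elsewhere, omitting uncomplicated Grade 3 thrombocytopenia and Grade 4 neutropenia of 5 days or less. Omitting Grade 3 anaemia is a fair design choice.
- **That the haemoglobin figures in 1.7.1 supply the rate.** That table is broken in extraction, pools Grades 3 and 4, and comes from repeated dosing at 8 GBq.
- **That the list certainly governs Part B.** It is written for Part A; its use in Part B is an inference.

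**Conclusion.** The gap is real on the text: treatment-related anaemia does not count by itself at any grade, and treatment-related death has no item of its own. It matters only for life-threatening or fatal events. The open formal rule is the last cohort's schedule rule, plus the Part B look if the same list is meant there.

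The size is small. There is no signal in 14 patients, and the pooled dose trigger is out of reach on the stated assumptions. The probabilities rest on an assumed anaemia rate. This is a point to consider, not a flaw that undermines the design.

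**What to change.** In 4.1.6 and the synopsis, add two DLT items: *Grade 4 treatment-related anaemia (excluding anaemia attributed to disease progression or to bleeding unrelated to treatment)* and *any treatment-related Grade 5 event*. In 8.3, state that the same list applies to the Part B look.

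No new data are needed, because all three study calendars already schedule blood counts on Days 1, 8 and 15 of Cycles 1 and 2. No event reported in 1.7.1 is reclassified: the count stays at 1 DLT in 14.

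The costs are a protocol amendment with review committee and IRB approval (9.4), and a slightly higher chance of meeting a trigger. Some of that extra chance would come from anaemia that is partly disease-driven, since the exclusion depends on judgement. Leaving out Grade 3 anaemia keeps it limited.

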6.1 Evaluation of efficacy (or Activity)

6.1.1 Definitions

Evaluable for toxicity

All patients will be evaluable for toxicity from the time of the first study drug administration.

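### As worded, Section 4.1.6 can remove an observed DLT from the 33% count when the patient later leaves the study for a non-toxicity reason before the end of Cycle 2

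*Combined protocol and SAP*

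**What the plan says.** The last paragraph of Section 4.1.6 covers two groups: "Patients who discontinue study for reasons other than treatment related toxicity during prior to the completion of two cycles of therapy", and those who leave before the priming dose. Both groups "will be considered inevaluable for purposes of DLT determination". For the first group, the only tests are when the patient left and why.

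The rules that depend on the count are in Sections 3.1 and 4.1.6:

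- **Cohort size.** "6 evaluable patients will be enrolled in each of the three cohorts in sequential fashion in Part A of the study".
- **Window.** "The DLT window will be Cycle 1 + Cycle 2", which the synopsis gives as six weeks from the Lu-PSMA-617 dose.
- **Schedule rule.** At a DLT frequency of 33% or more in a cohort, "that dosing schedule will be determined to be non-tolerable and the next schedule will be evaluated".
- **Dose rule.** If Lu-PSMA-617-attributable DLTs reach 33% "after 6 or more evaluable patients are enrolled in Part A of the study, accrual will be temporarily halted" and the dose goes to Dose Level -1.
- **Halting rule.** The same percentage at Dose Level -1 halts accrual.

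Two general statements bear on the point. Section 6.1.1 says: "All patients will be evaluable for toxicity from the time of the first study drug administration". Section 3.5 says that everyone who receives the priming dose is analyzed for study outcomes. Neither mentions the DLT count.

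On replacement, Section 3.5 covers "Subjects who withdraw from study participation prior to receiving dose of" Lu-PSMA-617. It does not mention patients who become inevaluable for DLT after that dose.

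**The concern.** An evaluability rule for DLTs normally exists because a patient who leaves early without a DLT has not been observed long enough to count as DLT-free. That reasoning does not apply to a patient who has already had a DLT, because the outcome is known. As written, Section 4.1.6 treats both patients alike.

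The sequence is possible in this trial. Lu-PSMA-617 is a single dose, and Section 6.3.2.5 attributes hematologic toxicity to it unless autoimmune cytopenia is clear. The mandatory stop for Grade 4 events in Section 4.8 concerns pembrolizumab-related events. A patient with Grade 4 thrombocytopenia attributed to Lu-PSMA-617 therefore has a DLT but need not leave the study because of it. The same patient could leave in week 5 for unequivocal clinical progression, withdrawal or compliance (Section 5.1), or for focal radiation to a symptomatic metastasis (Section 4.8, supportive care). On the literal text, the DLT then drops out of the count.

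What is at stake is the only numeric safety criterion in Part A. With 6 patients per cohort, a single event decides it.

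**Working it through.** The plan states no operating characteristics for the DLT rule, so there is no figure to reproduce.

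**1. Effect of one exclusion (no assumption about frequency).**

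- All counted: 2/6 = 33.3%. This meets the rule of 33% or more, and also the wording used elsewhere that the frequency exceeds 33%.
- One DLT patient excluded and not replaced: 1/5 = 20.0%.
- One DLT patient excluded and replaced by a patient without a DLT: 1/6 = 16.7%.
- Pooled dose rule at 18 patients, if all DLTs are attributable to Lu-PSMA-617: 6/18 = 33.3% becomes 5/17 = 29.4% or 5/18 = 27.8%.

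In each case the decision reverses.

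**2. When there is bias on average.** Let p be the true DLT rate. Let qd and qn be the probabilities of leaving for a non-toxicity reason within the window, for patients with and without a DLT. The DLT rate among counted patients is

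p(1 − qd) / [p(1 − qd) + (1 − p)(1 − qn)].

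If qd = qn, this equals p and there is no average bias. For example, p = 0.33 with both at 10% gives 0.330. The rate is too low only if qd > qn. Even without average bias, a known DLT is still discarded in the cohort where it occurs.

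**3. Size under stated assumptions.** The documents give neither qd nor qn. Assume p = 1/3, qn = 0, and replacement of excluded patients so that 6 are counted. Write e for the fraction of DLT patients excluded. The counted rate is r = p(1 − e)/(1 − pe), and the chance that the cohort is declared non-tolerable is

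P(at least 2 of 6) = 1 − (1 − r)^6 − 6r(1 − r)^5.

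| e (assumed) | r | P(at least 2 of 6) |
|---|---|---|
| 0 | 0.333 | 0.649 |
| 10% | 0.300/0.967 = 0.310 | 0.602 |
| 25% | 0.250/0.917 = 0.273 | 0.519 |
| 50% | 0.167/0.833 = 0.200 | 0.345 |

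At higher true rates the loss is similar in kind. With p = 0.40 the chance falls from 0.767 to 0.726 (e = 10%) or 0.466 (e = 50%). With p = 0.50 it falls from 0.891 to 0.864 or 0.649.

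**4. How often it could arise.** Cycles are 21 days, so C4D1 is Day 3 × 21 + 1 = 64. The first scheduled scan may be up to 14 days earlier, on Day 50. The DLT window ends at 6 weeks, or 42 days. Routine imaging therefore falls after the window. Section 7.6 agrees, at 9 weeks; the mention of Cycle 2 in Section 8.4.2 does not fit the study calendars. Section 3.4 also keeps patients with PSA-only progression on treatment. Non-toxicity exits within the window would thus come mainly from clinical progression, withdrawal, compliance or focal radiation.

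**The case against.** The strongest reply is that the sentence is garbled and was surely not meant this way. Section 4.1.6 defines a DLT by the event and its timing, Section 6.1.1 makes every treated patient evaluable for toxicity, and Section 3.5 analyzes everyone who receives the priming dose. As evidence of intent this is reasonable. It does not settle the count, because the general statements do not mention the DLT denominator and Section 4.1.6 is the specific rule.

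Several limits on size do stand:

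- A patient who leaves because of treatment-related toxicity remains evaluable. Section 4.8 requires permanent discontinuation for pembrolizumab-related Grade 4 events and several Grade 3 immune-related events, so many DLTs cannot be lost this way.
- The exclusion concerns leaving the study. A patient who stops treatment but attends the 30- and 90-day safety visits has not clearly left it.
- The exclusion fractions above have no source in the documents.
- A DLT outside the count is still recorded. Grade 3 to 5 events are reviewed monthly (Appendix 2), and Section 8.4.1 bases the recommended dose and schedule on aggregate safety and efficacy data. The numeric trigger is exposed; the event itself is not hidden.

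A reader might infer two stronger points that the documents do not support. The first is that rapid progression makes such exits common. Section 1.3 describes patients in a monotherapy study who did not complete four planned doses, for toxicity or for progression after initial response. It says nothing about exits within six weeks. The second is that Part A results are already distorted. Section 1.7.1 reports 14 patients enrolled by June 1, 2020, with one DLT, which was counted, and no Grade 3 or higher hematologic toxicity attributable to Lu-PSMA-617. It gives no sign of a dropped event.

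**Conclusion.** The rule is wrong as written, with moderate severity. Followed literally, Section 4.1.6 lets a known DLT leave the count, and in a cohort of 6 one such loss turns a non-tolerable schedule into a tolerable one. That reversal needs no assumption beyond the event occurring.

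The effect on average is conditional. It requires DLT patients to leave for other reasons more often than patients without a DLT. Under the assumptions in the table, the chance of flagging a schedule with a true DLT rate of 1/3 falls by about 5 percentage points at 10% exclusion and by about 30 points at 50%. The documents do not say where in that range the trial lies, and the scan timing suggests that the case is uncommon.

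The replacement wording is a secondary inconsistency. Section 3.5 provides replacement for patients who leave before Lu-PSMA-617, while Section 3.1 requires 6 evaluable patients. A reader might infer that cohorts will be judged on 5 patients, but the requirement for 6 evaluable already implies replacement. The two sections need to be aligned; this is not a further loss to add to the figures above.

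**What to change.** 1. **Section 4.1.6, last paragraph.** State that a patient who has a DLT in Cycle 1 or 2 is evaluable and counted as a DLT whatever the later reason for leaving. State that, among those who received the priming dose, only patients who leave for other reasons before the end of Cycle 2 without a DLT are inevaluable.
2. **Section 3.5.** State that patients who become inevaluable for DLT after Lu-PSMA-617 are replaced for the DLT cohort, and that they remain in the safety and efficacy sets. Cross-refer to Sections 3.1 and 6.1.1.
3. **Section 8.3.** Apply the same counting rule to the Part B look after 6 patients. That look uses DLT frequency but states no evaluability rule, and Section 4.1.6 is written for Part A.
4. **Part A DLT table.** Re-check it for any patient excluded after a DLT.

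The cost is a sentence or two in each of three sections and a review of a small table. No dose, DLT definition or threshold changes. The reported DLT frequency may be slightly less favourable. If some patients without a DLT leave and are replaced, the corrected rule leans slightly toward caution: with p = 0.33 and qn = 10%, the counted rate is 0.33/(0.33 + 0.67 × 0.90) = 0.354 and P(at least 2 of 6) is 0.688, against 0.642 when nobody leaves. That is an acceptable direction of error for a safety rule.
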